#### 9.4.2. Clinical Laboratory Evaluations

Laboratory test results (hematology, serum chemistry, and urinalysis) at each scheduled visit and change from baseline will be summarized by treatment group for Part A and Part B for Mainland Chinese patients or other patients separately.

Shift tables from baseline to each scheduled post-baseline visit will be provided for selected chemistry parameters (alanine aminotransferase [ALT], aspartate aminotransferase [AST], total bilirubin, creatinine, creatine kinase, alkaline phosphatase [ALP], potassium) and hematology parameters (hematocrit, hemoglobin, platelets, white blood cell count and differential). For chemistry parameters, the following categories will be used: < the lower limit of normal (LLN), normal, > the upper limit of normal (ULN) to ≤3×ULN, >3×ULN to ≤5×ULN, >5×ULN, and missing. For hematology parameters, the following categories will be used: low, normal, high, and missing.

The number and percentage (based on the number of patients with a normal level at baseline) of patients in each treatment group with an ALT (>3×ULN, >5×ULN, and >10×ULN), an AST (>3×ULN, >5×ULN, and >10×ULN), an ALT or AST >3×ULN, and a total bilirubin (>1.5×ULN and >2×ULN) will be presented by study visit. A listing of patients who meet the laboratory criteria for Hy’s law will also be provided. The laboratory criteria for Hy’s law is defined as concurrent ALT or AST>3×ULN, ALP ≤2.0×ULN, and total bilirubin >2×ULN. A listing will also be provided for the potentially clinically significant (PCS) values for the above parameters.

All clinical laboratory data will be listed. Values outside the normal ranges will be flagged.

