### **Safety:**

All patients who receive any amount of study drug (MITT Population) will be included in the safety analyses. Patients who received the wrong study drug for their entire course of treatment will be analyzed in the group based on the drug received.

A primary analysis of safety will be performed for Part A to assess the proportion of patients with nephrotoxicity, as measured by the RIFLE criteria based on the Safety and CE Populations.

---

---

Overall safety will be assessed for Part A and Part B in the Safety Population. The number and percentage of patients in each treatment group reporting at least 1 occurrence of a TEAE for each unique system organ class and preferred term will be tabulated. A TEAE is defined as an adverse event occurring on or after the administration of the first dose of study drug. Treatment-emergent adverse events will also be tabulated by treatment group, severity, and the relationship to study drug as assessed by the Investigator. The number and percentage of patients in each treatment group reporting at least 1 occurrence of a treatment-emergent serious adverse event will be tabulated. The number and percentage of patients (in each treatment group) prematurely discontinuing study drug treatment due to a TEAE will be tabulated by system organ class and preferred term. Adverse events of special interest in Part A will be summarized for all patients by treatment.

Safety laboratory data will be presented by descriptive statistics of the post-baseline value and the change from baseline, as well as the number and percentage of patients with potentially clinically significant laboratory values. Descriptive statistics of vital signs and ECG parameters and the change from baseline will also be presented. An outlier analysis of the ECG parameters will be conducted.

---

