#### **1.4 Risk/Benefit**

No unique contraindications have been determined for ETX2514. Contraindications to the use of sulbactam include a history of hypersensitivity or allergic reactions to sulbactam or any cephalosporin, penicillin, or carbapenem.

ETX2514 was well tolerated in repeat dose animal toxicology studies; no specific safety signals were observed that require special monitoring in human subjects. Reductions in absolute neutrophil count and monocytes were reported in the dog repeat dose toxicity studies and will be monitored by routine hematology assessments in human subjects.

Studies in healthy adult and elderly subjects and in patients with renal impairment or cUTI have revealed no serious adverse drug reactions or deaths to date, and the withdrawal rate due to adverse events has been low (1%). Adverse events have generally been mild to moderate in severity. The most common treatment-emergent adverse events (TEAEs) in both healthy elderly subjects and in patients have included injection site reactions/pain and headache; the less common TEAEs in patients were nausea, diarrhea, and vomiting. Overall, ETX2514SUL has been well tolerated, and only 1 drug-unrelated serious adverse event (SAE) has been reported to date. Doses of ETX2514SUL must be adjusted in patients with impaired renal function. Mild decreases from baseline in mean WBC and neutrophil counts have been observed in subjects receiving ETX2514 alone or multiple doses of ETX2514 with imipenem/cilastatin. Mild increases in alanine aminotransferase (ALT) were observed with administration of ETX2514SUL with imipenem/cilastatin. These findings were not considered clinically significant since mean values remained within the reference range at all time points. However, WBC counts and hepatic function will be monitored closely in ongoing clinical studies. No clinically significant changes in vital signs or ECG parameters have been observed in patients treated with ETX2514SUL with or without imipenem/cilastatin.

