#### 9.2.4 Analysis of Safety

All patients who receive any amount of study drug (MITT Population) will be included in the safety analyses. Patients who received the wrong study drug for their entire course of treatment will be analyzed in the group based on the drug received.

A primary analysis of safety will be performed for Part A to assess the proportion of patients with nephrotoxicity, as measured by the RIFLE criteria based on the Safety and CE Populations.

Overall safety will be assessed for Part A and Part B in the Safety Population. The number and percentage of patients in each treatment group reporting at least 1 occurrence of a TEAE for each unique system organ class and preferred term will be tabulated. A TEAE is defined as an adverse event occurring on or after the administration of the first dose of study drug. Treatment-emergent adverse events will also be tabulated by treatment group, severity, and the relationship to study drug as assessed by the Investigator. The number and percentage of patients in each treatment group reporting at least 1 occurrence of a treatment-emergent SAE will be tabulated. The number and percentage of patients (in each treatment group) prematurely discontinuing study drug treatment due to a TEAE will be tabulated by system organ class and preferred term. Adverse events of special interest in Part A will be summarized for all patients by treatment.

Safety laboratory data will be presented by descriptive statistics of the post-baseline value and the change from baseline, as well as the number and percentage of patients with potentially clinically significant laboratory values. Descriptive statistics of vital signs and ECG parameters and the change from baseline will also be presented. An outlier analysis of the ECG parameters will be conducted.

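### The SAP does not deliver the protocol's count of patients with potentially clinically significant laboratory values for hematology, so the laboratory tables cannot show how many patients per arm had a marked neutrophil or WBC decrease

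*SAP*

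**What the plan says.** **Protocol.** Section 9.2.4 says that laboratory data will be described by post-baseline value and change from baseline, "as well as the number and percentage of patients with potentially clinically significant laboratory values". The Safety paragraph of the synopsis makes the same commitment. Neither place names analytes or limits, and neither restricts the promise to liver tests.

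**SAP 9.4.2.**
- The last items in its set of threshold counts read "an ALT or AST >3×ULN, and a total bilirubin (>1.5×ULN and >2×ULN) will be presented by study visit". The others are graded ALT and AST cut-offs. Denominators are patients normal at baseline.
- For PCS values it says "A listing will also be provided for the potentially clinically significant (PCS) values for the above parameters".
- For shifts, "Shift tables from baseline to each scheduled post-baseline visit will be provided" for selected parameters, including "hematology parameters (hematocrit, hemoglobin, platelets, white blood cell count and differential", so neutrophils are covered. The categories are set by "For hematology parameters, the following categories will be used: low, normal, high, and missing".
- Values and changes from baseline are also summarized at each scheduled visit.

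**Why hematology matters here.** Protocol 1.4 states: "Mild decreases from baseline in mean WBC and neutrophil counts have been observed in subjects receiving ETX2514 alone", and also in subjects given multiple doses with imipenem/cilastatin. It reports neutrophil and monocyte reductions in dogs, and says that WBC counts and hepatic function will be monitored closely.

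**The concern.** A count by arm promised in the protocol has become, for hematology, at most a listing, and no hematology limit says what would enter it. The gap falls on a laboratory change that the protocol itself associates with the new drug. Liver tests, named beside WBC counts in the same monitoring sentence, receive graded cut-offs, counts and a Hy's law listing. WBC and neutrophils receive one undivided low category, visit by visit.

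At stake is a simple descriptive question: how many patients in each arm had a marked neutrophil or WBC decrease at any time after baseline? Part A is described as the first use of ETX2514SUL in intensive care patients, so readers of the report will ask it.

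**Working it through.** The plan states no figure on this point, so there is none to reproduce. The check is a comparison of texts, followed by an illustration under assumed rates.

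**1. Promise against delivery**

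| Item | Protocol 9.2.4 and synopsis | SAP 9.4.2 |
|---|---|---|
| Patients with PCS values, n (%) | Promised, no analytes named | ALT, AST and total bilirubin thresholds only |
| PCS limits for hematology | Left open | None stated |
| Grading below the lower limit of normal | Not addressed | None |
| Worst post-baseline value | Not addressed | Not used for laboratory data |

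SAP 9.4.4 does use a worst value for ECGs: it counts patients whose maximum QTcF over all post-baseline evaluations exceeds set limits.

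**2. Can by-visit shifts give the ever-low share?**

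The schedule of procedures has six scheduled post-baseline hematology visits: Day 3, Day 5, Day 7, EOT, TOC and LFU. Suppose a share r of patients is low at each visit, with everyone observed at all six.

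- Lower bound: the same patients are low each time, so the ever-low share is r.
- Upper bound: different patients are low each time, so the share is min(1, 6r).
- If visits were independent: 1 − (1 − r)^6.

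| Assumed r | Lower | Upper | Independent |
|---|---|---|---|
| 2% | 2% | 12% | 11.4% |
| 5% | 5% | 30% | 26.5% |
| 10% | 10% | 60% | 46.9% |

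The same by-visit tables fit a sixfold range of patient-level rates. Even the true ever-low share would not say how low the values went, because a count just under normal and a severe decrease share one category.

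**3. Would there be anything to count?**

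About 200 Part A patients randomized 1:1 gives about 100 per arm. The chance of at least one severe decrease in an arm is 1 − (1 − p)^100. For assumed true rates p of 1%, 2% and 5% this is 63%, 87% and 99%. These rates are illustrative; the documents give none.

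**4. Do other outputs fill the gap?**

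- *Adverse events.* Protocol 8.1 has clinically significant laboratory findings reported as adverse events. SAP 9.4.1 tabulates TEAEs as n (%) by preferred term and severity, once per patient at highest severity. Entry depends on the investigator's judgment, and Protocol 8.1.3 has the unblinded investigator rate severity by interference with daily activities, not by the count.
- *Descriptive summaries.* SAP 9.1.1 includes the minimum. That shows the single lowest value at each visit, not a number of patients.
- *Listings.* All laboratory data are listed with out-of-range values flagged. Counts could be made by hand, but not against a pre-specified limit.

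**The case against.** The strongest reply is that the signal is weak and already covered. Protocol 1.2 calls the reductions mild and reports no leukopenia or neutropenia events. Protocol 1.4 says that the changes were not considered clinically significant because means stayed within the reference range, and that the dog finding will be followed by routine hematology. Neutropenia is not an adverse event of special interest, and a promise of close monitoring is not a promise of a graded table. All of this stands, and it keeps the point minor.

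The PCS sentence can also be read as treating the liver tests as the PCS parameters, both counted and listed. That is possible, because the parameters it refers back to are not named. The protocol's wording is general, however, so the ambiguity itself needs resolving. The protocol does not promise counts for any particular non-liver analyte.

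Three stronger readings are tempting but unsupported:
- A reader might infer that neutropenia would have no severity analysis, or would appear in no table. The adverse-event route in SAP 9.4.1 rules that out for cases judged clinically significant, including those found at an unscheduled draw.
- A reader might infer that only liver tests are graded. Creatinine, creatine kinase, ALP and potassium have shift bands in multiples of the ULN, and RIFLE criteria cover renal function.
- A reader might infer that mean WBC change would be uninterpretable because WBC falls as infection resolves. Raised WBC is only one of several alternative entry signs, leukopenia is another, and randomization applies to both arms.

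**Conclusion.** The mismatch holds for hematology. The protocol commits to patient counts of PCS values; the SAP sets no hematology limit and gives no hematology count. Its by-visit low/normal/high shifts cannot recover the number of patients per arm with a marked WBC or neutrophil decrease at any time, and the adverse-event tables answer a narrower, judgment-based question.

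The text comparison needs no assumption. The illustration of size assumes equal by-visit rates and complete attendance; missed visits, or a Day 7 visit that doubles as EOT, would change the bounds but not the conclusion. The documents do not show that marked neutropenia is expected, and no arm difference is claimed.

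This is a minor supplementary safety point. It does not affect the primary efficacy or nephrotoxicity analyses.

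**What to change.** Reconcile SAP 9.4.2 with Protocol 9.2.4:

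1. Name the PCS parameters and pre-specify a limit for each. The sponsor should choose the limits, and they should serve reporting only, with no bearing on treatment or stopping. The neutrophil limit in the exclusion criteria is an eligibility limit; the documents set no analysis grades.
2. Report n (%) by arm and part of patients whose lowest post-baseline absolute neutrophil count and WBC cross those limits. Use all post-baseline values in the database, as SAP 9.4.4 does for maximum QTcF.
3. Add a baseline-to-worst shift table for the same two parameters.
4. State which parameters the PCS listing covers.

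The cost is SAP wording and one or two tables from hematology already collected, with no new sampling. One limit remains: Protocol 8.6 asks for local standard-of-care profiles but does not say that those results enter the database, so an unscheduled low value is captured only if it was recorded there.

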#### **9.4.3. Vital Signs**

Descriptive statistics will be provided for vital sign data (systolic and diastolic blood pressure, heart rate, and respiratory rate) presented as both actual values and changes from baseline over time by treatment group for Part A and Part B.

A listing of all vital signs will be provided by patient.

#### **9.4.4. Electrocardiograms (ECG)**

Descriptive statistics will be provided for 12-lead ECG findings (heart rate, QRS, PR, RR, QT, and QTcF) and changes from baseline for each scheduled visit for Part A and Part B. QTcF will be calculated as follows:

$$QTcF = \frac{QT}{\sqrt{RR}}$$

The number and percentage of patients with notable ECG changes in maximum QTcF (>450 msec, >480 msec, and >500 msec) over all post-baseline evaluations, as well as in QTcF maximum changes from baseline (>30 msec and >60 msec) over all post-baseline evaluations will be summarized by treatment group.

All ECG measurements and the overall interpretation will be listed by patient.

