13. Requirement for temporary or acute onset treatment with antiseizure medication that, in the opinion of the Investigator, would prohibit the patient from complying with the protocol. Patients at risk of seizure or requiring prophylactic antiseizure medications during the study can be considered for enrollment at the discretion of the Investigator. Patients with a history of epilepsy or who are on stable treatment (ie, no recurrent episodes in the past 30 days) and no history of imipenem-associated seizures may be considered for enrollment in the study;
14. Requirement for continuing treatment with probenecid, methotrexate, ganciclovir, valproic acid, or divalproex sodium during the study;
15. Evidence of significant hepatic disease or dysfunction, including known acute viral hepatitis, hepatic cirrhosis, hepatic failure, chronic ascites, or hepatic encephalopathy;
16. Aspartate aminotransferase (AST) or ALT >3 × upper limit of normal (ULN) AND total bilirubin >2 × ULN at Screening;
- Note: Patients with AST or ALT up to 5 × ULN are eligible if these elevations are acute and are documented as being directly related to the infectious process being treated.
17. Requirement at the time of randomization for any reason, or likely to require during the patient's participation in the study (from randomization through the LFU Visit), for additional systemic Gram negative antimicrobial therapy. See [Section 5.6.3](#) for a list of antibiotics that are allowed to treat mixed or concurrent infections;
18. Requirement for inhaled antibiotics;
19. Known history of human immunodeficiency virus infection and known recent CD4 count <200/mm^3 within the last year or presence of significant immunologic disease or dysfunction, as determined by a current diagnosis of an Acquired Immune Deficiency Syndrome-defining illness;
20. Presence of neutropenia (absolute neutrophil count <500/mm^3) obtained from a local laboratory at Screening;
21. A QT interval corrected using Fridericia's formula (QTcF) ≥480 msec;

22. History of significant hypersensitivity or allergic reaction to any BL, any contraindication to the use of cilastatin based on local approved prescribing information (eg, Summary of Medicinal Product Characteristics), any contraindication to the excipients used in the respective formulations, or any contraindication to the use of BL antibiotics;

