## LIST OF ABBREVIATIONS AND DEFINITIONS OF TERMS

Abbreviation	Definition
ABC	Acinetobacter baumannii-calcoaceticus complex
AE	Adverse event
ALP	Alkaline phosphatase
ALT	Alanine aminotransferase
AP	Acute pyelonephritis
APACHE	Acute Physiology and Chronic Health Evaluation
AST	Aspartate aminotransferase
ATC	Anatomical therapeutic class
BMI	Body Mass Index
BPP	Biofire FilmArray Pneumonia Panel
CE	Clinical Evaluable
CFU	Colony-forming units
CI	Confidence interval
COVID-19	Coronavirus Disease 2019
CRA	Clinical research associate
CRABC	Carbapenem-resistant Acinetobacter baumannii-calcoaceticus complex
CSR	Clinical Study Report
CT	Computed tomography
cUTI	Complicated urinary tract infection
DSMB	Data Safety Monitoring Board
ECG	Electrocardiogram
eCRF	Electronic case report form
EOT	End of Treatment
ESKD	End-stage kidney disease
ET	Early Termination
ETX2514SUL	Sulbactam-ETX2514
FiO2	Fraction of inspired oxygen
GFR	Glomerular filtration rate
HABP	Hospital-acquired bacterial pneumonia
ICF	Informed consent form
ICU	Intensive-care units
IRT	Interactive Response Technology
ITT	Intent-to-Treat
IV	Intravenous(ly)
LFT	Liver function test
LFU	Late Follow-up
LLN	Lower limit of normal

Abbreviation	Definition
ME	Microbiologic Evaluable
MedDRA	Medical Dictionary for Regulatory Activities
MIC	Minimum inhibitory concentration
MITT	Modified Intent-to-Treat
m-MITT	Microbiologically Modified Intent-to-Treat
MRI	Magnetic resonance imaging
PCS	Potentially clinically significant
PEEP	Positive end-expiratory pressure
PK	Pharmacokinetic(s)
q6h	Every 6 hours
q12h	Every 12 hours
qSOFA	Quick Sequential Organ Failure Assessment
QTcF	QT interval corrected using Fridericia's formula
RIFLE	Risk–Injury–Failure–Loss–End-stage renal disease
SAE	Serious adverse event
SAP	Statistical Analysis Plan
SOC	System organ class
SOFA	Sequential Organ Failure Assessment
TEAE	Treatment-emergent adverse event
TESAE	Treatment-emergent serious adverse event
TOC	Test of Cure
ULN	Upper limit of normal
VABP	Ventilator-associated bacterial pneumonia
VP	Ventilated pneumonia
WHO	World Health Organization

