### **6.5. Electrocardiograms**

Twelve-lead electrocardiograms (ECGs) will be performed for all patients at Screening, at the end of the first infusion of study drug on Day 1, at EOT, and at the ET Visit. If clinically indicated, the 12-lead ECGs will be repeated as close as possible following the end of the infusion of study drug on the day on which the post-dose PK samples are drawn (Day 4 [ $\pm$ 1 day]; day selected at the discretion of the Investigator). All 12-lead ECGs will be performed after the end of the infusion and after the patient has been in a supine position for at least 10 minutes. The value at Screening will be used for assessing the QT interval corrected using Fridericia's formula (QTcF) exclusion criterion. All 12-lead ECGs will be performed and read locally. The following ECG parameters will be recorded:

- Heart rate,
- QRS interval,
- PR interval,
- RR interval,
- QT interval, and
- QTc interval.

All ECGs will be evaluated for the presence of abnormalities by a qualified local physician. The ECGs will be classified as 1 of the following:

- Normal,
- Having a not clinically significant abnormality, or
- Having a clinically significant abnormality.

An example of a clinically significant abnormality may be a corrected QTcF  $\geq$ 480 msec.

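### The SAP's formula for QTcF divides QT by the square root of RR (the Bazett form), although both documents define QTcF as Fridericia's correction; the unit of RR is not given

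*SAP*

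**What the plan says.** SAP 9.4.4 gives an explicit rule: "QTcF will be calculated as follows", followed by QT divided by the square root of RR, with no root index shown and no unit for RR. The same section then counts patients by "maximum QTcF (>450 msec, >480 msec, and >500 msec) over all post-baseline evaluations", and by largest QTcF increase from baseline above 30 and above 60 msec.

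Elsewhere QTcF has one meaning. The SAP abbreviation list defines it as "QT interval corrected using Fridericia's formula". SAP 6.5 refers to the "QT interval corrected using Fridericia's formula (QTcF) exclusion criterion", and Protocol 4.2 sets that criterion as "A QT interval corrected using Fridericia's formula (QTcF) ≥480 msec". The Protocol's own abbreviation list agrees.

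On data capture, SAP 6.5 states that "All 12-lead ECGs will be performed and read locally". The recorded items include QT, RR and a QTc interval whose correction method is not named. Neither document prints another QTc formula.

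**The concern.** The label and the formula in SAP 9.4.4 cannot both be right. Fridericia's correction divides QT by the cube root of RR; dividing by the square root is Bazett's correction. The documents do not print the cube root, but it is what the named formula means.

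A programmer working from SAP 9.4.4 would apply the formula shown. The recorded QTc interval offers no safeguard, because its correction is unspecified and may differ between sites.

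Protocol 9.2.4 commits to an outlier analysis of ECG parameters, and SAP 9.4.4 is where that is carried out. A square root would inflate QTcF at heart rates above 60 bpm and deflate it below. It would also make the change from baseline depend on the change in heart rate. Patients could be counted as outliers when they are not, and true outliers could be missed.

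**Working it through.** **Inputs.** The formula and cut-offs come from SAP 9.4.4, and the Fridericia definition from SAP 6.5, the SAP abbreviation list and Protocol 4.2. The heart rates and QTcF values below are assumptions for illustration. The documents give no expected ECG values; the nearest is tachycardia above 100 bpm as one of the qualifying signs for bacteremia in Protocol 4.1.2. The plan states no numerical result to reproduce.

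**Ratio of the two forms.** With RR = 60 / heart rate, in seconds:

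- as printed: QT / RR^(1/2)
- Fridericia: QT / RR^(1/3)
- printed / Fridericia = RR^(1/3 − 1/2) = RR^(−1/6)

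A printed value of 480 msec therefore corresponds to a Fridericia value of 480 × RR^(1/6).

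| Heart rate (bpm) | RR (s) | Printed / Fridericia | Fridericia value that prints as 480 msec |
|---|---|---|---|
| 50 | 1.2 | 0.970 | 494.8 |
| 60 | 1.0 | 1.000 | 480.0 |
| 75 | 0.8 | 1.038 | 462.5 |
| 100 | 0.6 | 1.089 | 440.8 |
| 120 | 0.5 | 1.122 | 427.6 |

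The two forms agree only at 60 bpm.

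**Absolute cut-offs.** A Fridericia value F prints above a cut-off C once the heart rate exceeds 60 × (C / F)^6:

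- F = 420 prints above 450 from 60 × (450/420)^6 ≈ 91 bpm
- F = 450 prints above 480 from 60 × (480/450)^6 ≈ 88 bpm
- F = 480 prints above 500 from 60 × (500/480)^6 ≈ 77 bpm

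**Change from baseline, true Fridericia value constant at 420 msec.**

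- 60 to 100 bpm: 420 × (1.0889 − 1.0000) = +37.3 msec, falsely above 30
- 80 to 120 bpm: 471.4 − 440.6 = +30.8 msec, falsely above 30
- 75 to 100 bpm: 420 × (1.0889 − 1.0379) = +21.4 msec, which does not cross

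**Change from baseline, true rise with a falling heart rate.** Suppose the Fridericia value rises from 420 to 455 msec (+35) while the rate falls from 100 to 75 bpm. The printed values are 420 × 1.0889 = 457.3 and 455 × 1.0379 = 472.2, a change of +14.9 msec. A true increase above 30 msec is missed.

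**Units.** Take QT = 380 msec at 100 bpm. With RR = 0.6 s, the printed formula gives 491 and Fridericia gives 451. With RR = 600 msec, the printed formula gives 380 / √600 = 15.5. Only RR in seconds gives values on the scale of the cut-offs.

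**The case against.** The strongest reply is that the point hangs on one small character. In a text conversion of a PDF, a cube root and a square root differ only by the index on the radical, and a dropped index would not be an error in the plan. There is some sign of such loss: in the list of adverse events of special interest under SAP 9.4.1, the reference marker after Table 2 has been flattened to an ordinary digit. Against that, exponents survive elsewhere in the SAP, such as the colony-count limits in 5.5.2.1 and 9.2.4. Loss of the index is possible but not shown, so the source page has to be checked first.

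It can also be said that the intent is clear. Every definition names Fridericia, the variable is called QTcF, and Bazett is never mentioned. That is a good reason to expect a slip rather than a deliberate choice. It does not make the formula as it stands safe to program from.

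The missing RR unit is a minor matter. A result near 15 would be noticed at once.

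Finally, the output is descriptive, QTc prolongation is not an adverse event of special interest, and Protocol 1.2 reports a thorough QT study of ETX2514 in healthy volunteers with no clinically relevant effects. All of this limits the consequence. It does not justify a table labelled QTcF that holds a different quantity.

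**Conclusion.** The concern holds on the text as supplied. SAP 9.4.4 conflicts with the definition of QTcF in the Protocol and in the SAP itself, and no other formula in either document corrects it.

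If followed, the rule misstates QTcF by a factor of RR^(−1/6): about 3% too low at 50 bpm, 9% too high at 100 bpm and 12% too high at 120 bpm. It can create false outliers and hide true ones, both on the absolute cut-offs and on the changes from baseline. How many patients would be misclassified cannot be estimated without a heart-rate distribution.

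The effect is confined to the descriptive ECG safety tables. Eligibility rests on the locally read Screening ECG, and neither the primary analysis nor the sample size uses QTcF. The conclusion assumes that the formula in the source SAP is the same as in the supplied text. If the source shows a cube root, only the missing RR unit remains. Since this can be settled at almost no cost, it should be fixed before the ECG tables are produced.

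**What to change.** 1. Check the root index on the source page of SAP 9.4.4 and in the ECG analysis program.
2. If either uses a square root, replace it with QTcF = QT / RR^(1/3).
3. In either case, state that QT is in msec and RR in seconds.
4. State that this calculated value, not the site-reported QTc interval, is used for baseline and for every post-baseline ECG.

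The cost is a short edit to the SAP and, if needed, one line in the program. QT and RR are already recorded, so QTcF can be recomputed without new data.
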